#### 5.3.4. Health Outcome Measures

The AIM-D, Activity Level, and Activity Limitation will also be collected daily via an eDiary.

The MSQ v2.1 will be administered in an eTablet at specified visits.

AIM-D and MSQ v2.1 will be listed on mITT population.

##### 5.3.4.1. AIM-D

The AIM-D is an 11-item daily diary measure that assesses the impact of migraine and is comprised of two domains that evaluate performance of daily activities (7 items) and physical impairment (4 items). Participants are asked to rate the level of difficulty experienced in the past 24 hours with performance of daily activities (ie, difficulty with household chores, errands, leisure activities at home, leisure or social activities outside the home, strenuous physical activities, concentrating, and thinking clearly) and physical impairment (ie, difficulty walking, moving body, bending forward, and moving head) using a 6-point rating scale ranging from "Not difficult at all," "A little difficult," "Somewhat difficult," "Very difficult," "Extremely difficult," and "I could not do it at all." Three items include a response of "I did not . . .," for example, "I did not have errands planned." The AIM-D was developed as an electronic daily diary with the same set of questions administered in headache and non-headache versions. The Headache version is administered on days when a participant reports a headache and the Non-Headache version is administered on days when a participant does not report having a headache. The AIM-D instructs

participants to answer each question based on the level of difficulty experienced in the past 24 hours for both versions, with “during your headache” indicated for the AIM-D Headache. In addition to the two domain scores, a total score using all 11 items can also be calculated. Each raw daily domain score, as well as the raw daily total score, are transformed to a 0-100 scale, with higher scores indicating greater impact of migraine (i.e., higher disease burden).

Two items based on a 24-hour recall will be administered daily using Headache and Non headache versions as additional health outcome measures and for evaluation of the AIM-D. The first item will be used to assess activity level within the past 24 hours with a 5 level response scale ranging from “No activity – Spent all day lying down” to “Exercised – Brisk walk, running, jogging, biking or other activity for 30 or more minutes.” The second item will be used to evaluate activity limitation with a 5-level response scale ranging from “Not at all limited – I could do everything” to “Extremely limited”.

Overall satisfaction with the study medication for prevention of migraine will be assessed using a single item and a 7-point rating scale ranging from extremely satisfied (0) to extremely dissatisfied (6).

#### **5.3.4.2. MSQ**

The MSQ v2.1 is a 14-item questionnaire designed to measure health-related quality-of-life impairments attributed to migraine in the past 4 weeks. It is divided into three domains: Role Function-Restrictive assesses how migraines limit one’s daily social and work-related activities; Role Function-Preventive assesses how migraines prevent these activities; and the Emotional Function domain assesses the emotions associated with migraines. Participants respond to items using a 6-point scale ranging from “none of the time” to “all of the time.” Raw dimension scores are computed as a sum of item responses and rescaled to a 0 to 100 scale, where higher scores indicate better quality of life.

The detailed algorithms for derivation of the above health outcome measures are presented in Section 6.4.3

### **5.4. Other Safety Analyses**

#### **5.4.1. Extent of Exposure**

Treatment daily dose will be listed on Safety Population.

#### **5.4.2. Treatment Compliance**

Dosing compliance for a specified period is defined as the total number of open-label study interventions actually taken by a participant during that period divided by the number of open-label study interventions that were expected to be taken during the same period multiplied by 100. The total number of tablets actually taken during a specific period will be calculated from the study intervention record. Treatment compliance and duration will be listed for the Safety population.

### 5.4.3. Adverse Events

Adverse events (AEs) will be coded using the Medical Dictionary for Regulatory Activities (MedDRA) version 22.1 or higher.

An AE will be considered as a treatment-emergent adverse event (TEAE) if the AE began or worsened (increased in severity or became serious) on or after the date of the first dose of double-blind study treatment in the lead-in study. An AE that occurs more than 30 days after the last dose of open-label study treatment or the safety follow-up visit (Visit 5) in this extension study whichever comes later will not be counted as a TEAE. Per case report form instructions, a new AE record will be created for any AE that worsens; therefore, TEAEs can be identified as those AEs captured in Study 3101-311-002 with recorded onset date on or after the date of the first dose of lead-in double-blind study treatment and within 30 days after the last dose of open-label study treatment or Visit 5 whichever comes later.

An AE will be considered as a treatment-emergent SAE (TESAE) if it is a TEAE that also meets SAE criteria.

TEAEs that started after the date of last dose of open-label study treatment will be considered as newly emergent TEAEs (NEAE).

Only TEAEs that started on or after the date of first dose of open-label study treatment will be summarized.

AEs will be listed on the Safety Population.

### 5.4.4. Additional Safety Assessments

#### 5.4.4.1. Clinical Laboratory Parameters

Laboratory parameters in standard units at each assessment time point will be listed by study intervention group for the following laboratory parameters:

Category	Parameter
Chemistry	Sodium, potassium, chloride, bicarbonate, glucose, blood urea nitrogen, creatinine, total bilirubin, alkaline phosphatase, aspartate aminotransferase, alanine aminotransferase, lactate dehydrogenase, creatine kinase, total protein, albumin, calcium, phosphorus, uric acid, total cholesterol, the estimated glomerular filtration rate
Hematology	Hemoglobin, hematocrit, red blood cell count, red blood cell indices (mean corpuscular volume, mean corpuscular hemoglobin, mean corpuscular hemoglobin concentration), white blood cell count, including differential (neutrophils, lymphocytes, monocytes, eosinophils, and basophils), platelet count
Urinalysis	Specific gravity, pH

Clinical laboratory test values will be considered potentially clinically significant (PCS) if they meet either the lower-limit or higher-limit PCS criteria listed in Section 6.3.7.2. PCS laboratory values will be listed.

Participants with an adjudicated case (i.e. ALT  $\geq 3 \times$  ULN or AST  $\geq 3 \times$  ULN) will be listed with their ALT and AST assessments, adjudication dates, relationship of ALT or AST elevation to study intervention, and confounding factor(s). Additional listings will be provided for participants who meet ALT  $\geq 3 \times$  ULN or AST  $\geq 3 \times$  ULN and/or potential Hy's law and have one of the following categories: at least 1 abnormal liver biochemistry risk factor, at least 1 liver disease sign and symptom, at least 1 liver diagnostic test performed, consultation with a specialist for liver evaluation, liver lab tests performed, and drug screen performed, respectively.

Potential Hy's Law criteria within a 24-hour window is defined by a post baseline elevation of alanine aminotransferase (ALT) or aspartate aminotransferase (AST)  $\geq 3 \times$  ULN, along with total bilirubin (TBL)  $\geq 2 \times$  ULN and a non-elevated alkaline phosphatase (ALP)  $< 2 \times$  ULN, all based on blood draws collected within a 24-hour period.

#### 5.4.4.2. Vital Signs

Listings for vital signs (systolic and diastolic blood pressures [sitting and standing], pulse rate [sitting and standing], respiratory rate, temperature, weight, orthostatic systolic blood pressure, orthostatic diastolic blood pressure, and orthostatic pulse rate) at each assessment timepoint will be listed. Orthostatic vital sign values (orthostatic systolic and diastolic blood pressures, and orthostatic pulse rate) are defined as the corresponding standing measurement minus sitting measurement of systolic and diastolic blood pressures and pulse rate respectively.

Vital sign values will be considered PCS if they meet both the observed value criterion and the change from baseline value criterion, if both criteria are available, or meet either the observed value criterion or the change from baseline value criterion that will be detailed in Section 6.3.7.4. Participants who have PCS postbaseline vital sign values will be listed.

#### 5.4.4.3. Electrocardiogram

Listings for ECG parameters (ie, heart rate, PR interval, QRS interval, RR interval, QT interval, and QTc interval) at each assessment timepoint will be presented. The QTc will be calculated using both the Fridericia correction and the Bazett correction.

ECG parameter values are considered PCS if ECG values meet either the actual value or change from baseline PCS high criteria listed in [Table 6-5](#). Participants with PCS postbaseline values will be listed.

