### 6.3.7.2. Potentially Clinically Significant Criteria for Clinical Laboratory Parameters

Table 6-3 Potentially Clinically Significant Criteria for Clinical Laboratory Parameters

Category	Parameter	SI Unit	PCS Criteria	
			PCS Low	PCS High
Chemistry	Albumin	g/L	< 0.8 × LLN	> 1.2 × ULN
	Alanine aminotransferase	U/L	—	≥ 3.0 × ULN
	Alkaline phosphatase	U/L	—	≥ 3.0 × ULN
	Aspartate aminotransferase	U/L	—	≥ 3.0 × ULN
	Bicarbonate	mmol/L	< 0.9 × LLN	> 1.1 × ULN
	Bilirubin, total	μmol/L	—	≥ 1.5 × ULN
	Blood urea nitrogen	mmol/L	—	≥ 1.5 × ULN
	Calcium	mmol/L	< 0.9 × LLN	> 1.1 × ULN
	Chloride	mmol/L	< 0.9 × LLN	> 1.1 × ULN
	Cholesterol, total	mmol/L	—	> 1.6 × ULN
	Creatinine	μmol/L	—	≥ 1.5 × ULN
	Creatine kinase	U/L	—	> 2.0 × ULN
	Estimated glomerular filtration rate	mL/min/1.73m 	< 60	—
	Glucose, nonfasting	mmol/L	< 0.8 × LLN	> 2.0 × ULN
	Lactate dehydrogenase (LDH)	U/L	—	≥ 3.0 × ULN
	Phosphorus	mmol/L	< 0.9 × LLN	> 1.1 × ULN
	Potassium	mmol/L	< 0.9 × LLN	> 1.1 × ULN
	Protein, total	g/L	< 0.9 × LLN	> 1.1 × ULN
Hematology	Sodium	mmol/L	< 0.9 × LLN	> 1.1 × ULN
	Uric acid	μmol/L	—	> 1.2 × ULN
	Basophils, absolute cell count	10  /L	—	> 2.0 × ULN
	Eosinophils, absolute cell count	10  /L	—	> 2.0 × ULN
	Hematocrit	Ratio	< 0.9 × LLN	> 1.1 × ULN
	Hemoglobin	g/L	< 0.9 × LLN	> 1.1 × ULN
	Lymphocytes, absolute cell count	10  /L	< 0.7 × LLN	> 1.3 × ULN
	Monocytes, absolute cell count	10  /L	< 0.5 × LLN	> 2.0 × ULN
	Neutrophils, absolute cell count	10  /L	< 0.7 × LLN	> 1.3 × ULN
Urinalysis	Platelet count	10  /L	< 0.5 × LLN	> 1.5 × ULN
	Red blood cell count	10  /L	< 0.9 × LLN	> 1.1 × ULN
	White blood cell count	10  /L	< 0.9 × LLN	> 1.5 × ULN
	pH	pH	< 0.9 × LLN	> 1.1 × ULN
	Glucose	mmol/L	—	At least 1+
	Protein	g/L	—	At least 1+
	Specific gravity	—	—	> 1.1 × ULN

LLN = lower limit of normal value; ULN = upper limit of normal value; normal value provided by laboratory.

SI = Le Système International d'Unités (International System of Units).

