#### 6.3.7.4. Potentially Clinically Significant Criteria for Vital Signs

Table 6-5 Potentially Clinically Significant Criteria for Vital Signs

Parameter	Flag	Criteria	
		Observed Value	Change from Baseline
Systolic blood pressure, mm Hg	High	$\geq 180$	Increase of $\geq 20$
	Low	$\leq 90$	Decrease of $\geq 20$
Diastolic blood pressure, mm Hg	High	$\geq 105$	Increase of $\geq 15$
	Low	$\leq 50$	Decrease of $\geq 15$
Pulse rate, bpm	High	$\geq 120$	Increase of $\geq 15$
	Low	$\leq 50$	Decrease of $\geq 15$
Weight, kg	High	—	Increase of $\geq 7\%$
	Low	—	Decrease of $\geq 7\%$
Orthostatic SBP change, mm Hg	Low	$\leq -20$	—
Orthostatic DBP change, mm Hg	Low	$\leq -15$	—
Orthostatic Pulse rate change, bpm	High	$\geq 25$	—

SBP = Systolic blood pressure, DBP = Diastolic blood pressure, bpm = beats per minute.

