#### 6.3.7.5. Potentially Clinically Significant Criteria for ECG parameters

Table 6-6 Potentially Clinically Significant Criteria for ECG parameters

Parameter	Unit	Criterion
QRS interval	msec	$\geq 150$
PR interval	msec	$\geq 250$
QTc (QTcB or QTcF) interval	msec	$> 500$
QTc (QTcB or QTcF) interval	msec	Increase from baseline $> 60$

QTc = QT interval corrected for heart rate.

QTcB = QT interval corrected for heart rate using the Bazett formula.

QTcF = QT interval corrected for heart rate using the Fridericia formula.

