**6.4.10. Character Values of Clinical Laboratory Parameters**

If the reported value of a clinical laboratory parameter cannot be used in a statistical summary table because, for example, a character string is reported for a parameter of the numeric type, a coded value must be appropriately determined for use in the statistical analyses. The actual values, however, as reported in the database will be presented in the data listings.

[Table 6-11](#) shows examples of how some possible laboratory results should be coded for the analysis.

Table 6-11 Examples of Coding Special Character Values for Clinical Laboratory Parameters

Laboratory Test, SI Unit	Possible Laboratory Results	Coded Value for Analysis
CHEMISTRY		
ALT, U/L	< 5	5
AST, U/L	< 5	5
Bilirubin, total, $\mu$ mol/L	< 2	2
URINALYSIS		
Glucose, mmol/L	= OR $> 55, \geq 55, > 0$	Positive
	$\leq 0$ , negative	Negative
pH	$> 8.0, \geq 8.0$	8.0
	$\geq 8.5$	8.5
Protein	= OR $> 3.0, \geq 3.0, > 0$	Positive
	$\leq 0$	Negative

ALT = alanine aminotransferase; AST = aspartate aminotransferase; SI = *Le Système International d'Unités* (International System of Units).

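### Two SAP rules for potentially clinically significant values do not work as written: the ECG rule cites the vital-signs table, and the urine specific gravity limit cannot be reached

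*SAP*

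**What the plan says.** **ECG.** SAP Section 5.4.4.3 treats an ECG value as PCS when it meets either the observed-value or the "change from baseline PCS high criteria listed in [Table 6-5". Section 6.3.7.4 contains "Table 6-5 Potentially Clinically Significant Criteria for Vital Signs". The ECG limits follow in Section 6.3.7.5, under "Table 6-6 Potentially Clinically Significant Criteria for ECG parameters".

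**Urine specific gravity.** The row in Table 6-3 (Section 6.3.7.2) reads "Specific gravity — — > 1.1 × ULN": no unit, no low limit, and one high limit expressed as a multiple of the ULN. The table footnote leaves the limits of normal to the laboratory ("normal value provided by laboratory"), and neither document gives a figure.

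**Urine glucose and protein.** Table 6-3 gives concentration units but a dipstick grade as the criterion, for example "Glucose mmol/L — At least 1" followed by a plus sign. Section 6.4.10 says that where a result cannot enter a summary table, "a coded value must be appropriately determined for use in the statistical analyses". Its Table 6-11 gives examples in which glucose and protein results become Positive or Negative.

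**The concern.** A PCS rule is a pre-specified screen: it decides which participants are pulled out of the full data for attention. Safety is the primary objective, and SAP Section 6.2 (item 5) removes the summaries of change from baseline for laboratory, vital-sign and ECG values. The PCS listings therefore carry more of the reporting than they did before.

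If a rule cannot fire, its listing is empty whatever the data show. Someone reading the study report could take an empty ECG or specific gravity PCS listing as reassurance, when it would only reflect how the rule was written.

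**Working it through.** The plan states no figure to reproduce here. The check is a comparison of tables for the ECG rule and simple arithmetic for specific gravity.

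**Step 1. ECG rule against the two tables.**

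| ECG criterion (Table 6-6) | Row in Table 6-5, the table cited? |
|---|---|
| QRS interval ≥ 150 msec | No |
| PR interval ≥ 250 msec | No |
| QTc > 500 msec | No |
| QTc increase from baseline > 60 msec | No |

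The rows of Table 6-5 are systolic and diastolic blood pressure, pulse rate, weight, and the orthostatic changes in systolic pressure, diastolic pressure and pulse rate. Through the cited table, 0 of the 4 ECG criteria are reached.

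A side effect is possible. Section 5.4.4.3 also lists ECG heart rate. If a programmer matched it to the pulse row, the either/or wording would flag a rise of ≥ 15 bpm alone. Section 5.4.4.2 requires both criteria for pulse, and Table 6-6 has no heart-rate limit.

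**Step 2. Specific gravity limit.** Inputs:

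- Multiplier 1.1, from Table 6-3.
- ULN: not in the documents; assumed 1.020 to 1.050.
- Start of the scale: about 1.000 (water).
- Highest recordable value: not in the documents; assumed 1.035 to 1.060.

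Formula: limit = 1.1 × ULN. The last column is (limit − 1) / (ULN − 1), the number of times the excess over water at the ULN that a flag would require.

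| Assumed ULN | Limit | Multiple of excess over water |
|---|---|---|
| 1.020 | 1.122 | 6.1 |
| 1.030 | 1.133 | 4.4 |
| 1.040 | 1.144 | 3.6 |
| 1.050 | 1.155 | 3.1 |

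The lowest limit in the table, 1.122, exceeds the highest assumed recordable value, 1.060. Even a ULN of 1.000 would give 1.1 × 1.000 = 1.100.

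In reverse, a flag needs ULN < maximum / 1.1. For a maximum of 1.035 this is 0.941, and for 1.060 it is 0.964. Both are below water.

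**Step 3. Urine glucose and protein.** Table 6-3 asks for a grade of 1+ or more, while its unit column and the Table 6-11 examples are mainly in concentrations. Nothing in the SAP maps 1+ to mmol/L or g/L. A two-level Positive/Negative variable with its cut at zero could not be used to judge 1+. The SAP does not say whether PCS status is taken from the reported result or from a coded one.

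**The case against.** The strongest reply on the ECG rule is that it is one wrong table number. Section 6.3.7 announces separate ECG criteria, Table 6-6 is titled for ECG, and its observed-value and change-from-baseline rows fit the wording of Section 5.4.4.3. No rival ECG table exists, so a careful programmer would probably choose correctly. That stands as to the likely outcome. It does not make the text right, because an operative flagging rule should not depend on a guess.

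The second reply is that nothing is hidden, and this largely stands. ECG values are listed at each timepoint (SAP 5.4.4.3), as is specific gravity (5.4.4.1), and Section 6.4.4 puts all assessments in the listings. SAP Section 3 expects about 3 participants and the schedule has ECGs at 3 visits, so about 3 × 3 = 9 scheduled ECGs. A cardiologist reads each ECG centrally and the investigator judges its significance (protocol 6.1.6). The investigator also assesses out-of-range laboratory values (protocol 6.1.3). An extreme value would be found by eye.

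The third reply is that the specific gravity result rests on laboratory figures that the documents do not give. That is true, but the conclusion is the same over the whole assumed range.

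**Conclusion.** Both rules need correcting. The ECG error is certain and needs no assumption. The specific gravity limit is unreachable for any ULN of at least 1.000, provided the highest recordable value is below 1.100; the assumed range is 1.035 to 1.060.

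The size is small. The errors affect which participants appear in the PCS listings. They do not affect the data, and no inference is at stake because the study has no statistical hypothesis.

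A reader might infer more, but the documents do not support it:

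- **That the PCS rules fail in general.** The chemistry, hematology and vital-signs criteria are not in question here.
- **That PCS listings are the only place where abnormal safety values are singled out.** Section 5.4.4.1 has separate listings for ALT or AST elevations and potential Hy's law cases, and Section 5.4.4.4 lists suicidal ideation and behavior.
- **That the urine glucose or protein grade is lost from the data.** The Table 6-11 coding is conditional and given as examples, none of which shows a graded result being recoded. Section 6.4.10 keeps reported values in the listings. What is missing is only a statement of which value the rule uses.
- **That the high limit for urine pH is equally unreachable.** Table 6-11 recodes only censored results such as those reported as above 8.0, and it does not cap numeric ones. The answer also turns on the ULN: an assumed 8.0 gives 1.1 × 8.0 = 8.8, but 7.5 gives 8.25, which a coded 8.5 exceeds.

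**What to change.** 1. In SAP Section 5.4.4.3, replace the reference to Table 6-5 with Table 6-6.
2. In Table 6-3, either delete the specific gravity row and list out-of-range values, or replace the multiple of ULN with an absolute limit taken from the central laboratory's reporting scale.
3. In the same edit, as a minor clarification, state that PCS status for urine glucose and protein is judged on the reported dipstick grade and not on any Positive/Negative coding.

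The cost is a short SAP revision and a small programming change, with no new data. The downside is that a few more values may be flagged.

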#### 5.4.4.4. Columbia-Suicide Severity Rating Scale

For C-SSRS, participants with suicidal ideation or suicidal behavior as recorded on the C-SSRS will be listed for the Safety population.

### 5.5. Interim Analyses

No interim analysis is planned.

## 6. Supporting Documentation

### 6.1. Appendix 1 List of Abbreviations

Term/ Abbreviation	Definition
AE	adverse event
AIM-D	Activity Impairment in Migraine – Diary
ALT	alanine aminotransferase
AST	aspartate aminotransferase
BP	blood pressure
CM	chronic migraine
CNS	central nervous system
C-SSRS	Columbia-Suicide Severity Rating Scale
DBP	diastolic blood pressure
ECG	electrocardiogram
eCRF	electronic case report form
eDiary	electronic diary
ET	early termination
eTablet	electronic tablet
IWRS	interactive web response system
MedDRA	Medical Dictionary for Regulatory Activities
miITT	modified intent-to-treat
MSQ v2.1	Migraine Specific Quality of Life Questionnaire, version 2.1
NEAE	newly emergent TEAE (NEAE)
PT	preferred term
QD	once daily
QTcF	QT interval corrected for heart rate using the Fridericia formula
QTcB	QT interval corrected for heart rate using the Bazett formula
SAE	serious adverse event
SBP	systolic blood pressure
SOC	system organ class
TEAE	treatment-emergent adverse event
ULN	upper limit of normal

## 6.2. Appendix 2: Changes to Protocol-Planned Analyses

The following changes to the Protocol amendment 1 were made in this SAP:

1. Section 7.2.2 of the protocol amendment 1 stated that “The related health outcome analyses will be documented in the health economics and outcomes research statistical analysis plan.” Instead, these health outcome analyses are added to this SAP document.
2. Removed following efficacy variables:
  - Change from baseline in monthly headache days at each monthly period.
  - Change from baseline in monthly acute medication use days at each monthly period.
  - $\geq 25\%$ ,  $\geq 50\%$ ,  $\geq 75\%$ , and 100% improvement (decrease) in monthly migraine days at each monthly period.
  - Change from baseline in monthly cumulative headache hours at each monthly period
  - Change from baseline in monthly triptan use days at each monthly period
  - Change from baseline in monthly moderate/severe headache days at each monthly period
  - Change from baseline in monthly severe headache days at each monthly period.
  - Other Health Outcome endpoints (see Section 5.3.1)
3. Efficacy variables will be listed, and will not be summarized.
4. Removed following demographic table summaries. Where noted in the body of the SAP, data will be presented in listings:
  - Analysis populations
  - Summary of enrollment category
  - Concomitant medication during the follow-up period
5. Removed following safety summaries. Where noted in the body of the SAP, data will be presented in listings:
  - TEAEs by SOC, PT and severity
  - NEAEs
  - Common ( $\geq 2\%$ ) TEAEs by PT
  - Summary of baseline, post-baseline, and change from baseline in laboratory parameters
  - Summary of baseline, post-baseline, and change from baseline in vital signs
  - Summary of baseline, post-baseline, and change from baseline in ECG

